6.3.1 Columbia-Suicide Severity Rating Scale

The C-SSRS monitors changes in suicidal thinking and behavior over time, in order to determine risk (Posner et al. 2011). The following four constructs are measured: the severity of ideation, the intensity of ideation, behavior, and lethality.

The C-SSRS will be used to assess suicidal ideations and behaviors; the Baseline/Screening version will be administered at Screening, and the Since Last Visit version will be administered at subsequent visits. The C-SSRS results for each subject should be reviewed by the Investigator at each visit. If at any time the C-SSRS results for a given subject reveal potential suicidality, then the Investigator should assess the clinical significance of such results. If a clinically significant risk of suicidality is identified for a subject, then the Investigator should discontinue the subject and implement appropriate treatment (Sections 4.4 and 3.1.3).

The C-SSRS will be administered at Screening and Baseline, at all visits from Week 1 through Week 6, and at unscheduled visits.

The same rater or clinician should perform the C-SSRS together with the same caregiver throughout the study as established at Baseline visit.

6.3.2 **Extrapyramidal Symptom Rating Scale-Abbreviated**

The ESRS (Chouinard and Margolese 2005) was developed to assess drug induced movement disorders such as parkinsonism, akathisia, dystonia, and tardive dyskinesia with established reliability, validity, and sensitivity. It consists of a questionnaire of parkinsonian symptoms, physician examination of parkinsonism, dyskinetic movements, and global impression of tardive dyskinesia. The ESRS-A, an accepted modified form of the original ESRS, will be used during the study to monitor for any worsening in extrapyramidal symptoms or signs at scheduled and unscheduled visits.

The ESRS-A will be administered at Screening and Baseline; at all visits from Week 1 through Week 6; and at unscheduled visits. The ESRS-A will only be conducted at clinic visits and not at remote visits.

The same rater or clinician should perform the ESRS-A together with the same caregiver throughout the study as established at Baseline visit.

6.4 Safety Assessments

As known potential class side effects of antipsychotics, the following adverse events will be actively monitored, including hyperglycemia, leucopenia/neutropenia/agranulocytosis, orthostatic hypotension/bradycardia/syncope, QTc prolongation, akathisia and other extrapyramidal symptoms, weight gain, and somnolence. Criteria for identifying potentially clinically important laboratory values, ECG values, and vital signs are presented in Appendix C, Appendix D, and Appendix F, respectively; and criteria for identifying additional ECG measurements of potential clinical relevance for Medical Monitoring purposes are presented in Appendix E.

Circumstances may arise (e.g., pandemic, natural disaster, political upheaval, or technical issues) when on-site assessments of safety measures may not be possible. In those cases, assessments may be performed at the subject's place of residence either in person or via video technology or telephone, where possible. If a subject is unable to come to the site for lab draws and the site is unable to travel to the subject's place of residence, the subject may visit a local lab to obtain all safety labs. The Investigator must contact the Medical Monitor for approval with the plan. Sites must keep a log to identify details of all visits that are administered remotely.

6.4.1 Medication History

Current and past treatments, medication history, or therapies that are specific to their diagnosis will be recorded. A careful review of current, recent, and past medications with each subject will also be performed. Medication history will be collected at the Screening and Baseline visits

6.4.2 Physical Examination

A general physical examination will be conducted at Screening and Baseline, at Week 3 and Week 6 visits.

Height will be measured and reported.

Weight will be measured and reported.

Body mass index will be calculated using the following formula:

Weight $(kg) / [height (m)]^2$.

Height (as measured by a stadiometer) and weight will also be measured at all visits from Week 1 through Week 6, and at unscheduled visits. Height and weight measurements are optional at the Week 2 and Week 5 visits if these are conducted remotely.

Final Version: 1.0

6.4.3 Vital Signs

Vital signs will include body temperature, resting respiration rate, sitting (or supine) systolic and diastolic blood pressure, and pulse rate.

The sitting (or supine) blood pressure should be measured after the subject has been sitting (or supine) for ≥ 3 minutes. If the initial blood pressure measurement is:

- ≥90th percentile systolic and/or diastolic for gender-specific age and height charts from the National Heart and Lung Institute (NHLI) for subjects under 13 years or
- \geq 120 mmHg systolic or \geq 80 mmHg diastolic for subjects 13 through 17 years,

at least 5 minutes rest should be allowed after the first measurement; then two additional blood pressure measurements are to be performed consecutively. The average of the three blood pressure measurements, systolic and diastolic, is the final blood pressure measurement and this average is the one to be entered into the EDC. All of the three blood pressure measurements with documentation of the time starting the resting and the time at which the two additional blood pressures are measured should be source documented.

If the subject is reporting symptoms of orthostatic hypotension when standing up after the blood pressure measurement, then the subject will be asked to lie down for 5 minutes, blood pressure and pulse rate will be measured, then the subject will be asked to stand and blood pressure and pulse rate measurements will be repeated after standing 1 to 3 minutes in order to measure the severity of the orthostatic hypotension. Vital signs will be collected at Screening and Baseline, at all visits from Week 1 through Week 6, and at unscheduled visits. Vital signs are optional at the Week 2 and Week 5 visits if these are conducted remotely.

6.4.4 Electrocardiograms

All 12-lead electrocardiograms (ECGs) will be complete, standardized recordings, performed in sequential triplicate whenever possible at Screening, Baseline, Week 3, and Week 6 (EOT/ET). The involvement of experienced personnel in the conduction of ECG recording in this population is strongly recommended.

Electrocardiograms should be performed before blood sampling or at least 30 minutes after blood sampling. The subject must rest in a sitting or supine position for 5 minutes before the ECG is obtained. Mild sedation is allowed exceptionally for ECGs (e.g., alprazolam at a pediatric-appropriate dose per age, and the *lowest dose* deemed necessary by the Investigator) just in cases when the subject's agitation/anxiety does not allow a safe and accurate measurement and the Investigator, with agreement from the caregiver, considers it safe and appropriate for the subject. ECG tracings (paper or electronic) will be reviewed and

Final Version: 1.0 Clinical Study Protocol Amendment 4 Date: 21 December 2022

interpreted by a qualified clinician. ECG tracings and results (ventricular rate, PR, QRS, QT, QTcF, and QTcB intervals) will be included in the subject's study records.

Eligibility at Baseline should be based on ECG tracings collected on the study-provided ECG device during the visit and on the ECG central read. All ECGs will be centrally read; the cardiology central overread is considered final. The QTcF/QRS as well as other exclusionary values and abnormalities of all the tracings of adequate quality will be reviewed to determine eligibility.

A maximum of one repeat ECG procedure is allowed that can occur either at Screening or Baseline.

- If the ECG was repeated during the Screening period and the central ECG read during Baseline evaluation contains any of the exclusionary abnormalities, the subject should be withdrawn from study
- If the ECG was not repeated at Screening and the central ECG read at Baseline contains any of the exclusionary abnormalities, the Baseline ECG may be repeated.

6.4.5 **Laboratory Evaluations**

Clinical laboratory sample collection (including HbA_{1c}) is encouraged, but not required to be completed under fasting conditions. The laboratory evaluations will include, but are not limited to, the following:

- Clinical chemistry serum tests
 - o Sodium (Na), potassium (K), carbon dioxide (CO₂), chloride (Cl), phosphorus (P), calcium (Ca), blood urea nitrogen (BUN), creatinine (CR), glucose, albumin (ALB), total protein
 - o Alanine aminotransferase (ALT), aspartate aminotransferase (AST), gamma-glutamyl transpeptidase (GGT), alkaline phosphatase (ALP), total bilirubin (TBIL), lactate dehydrogenase (LDH)
 - Lipid panel
 - Total cholesterol, high-density lipoprotein (HDL)-cholesterol, triglycerides, low-density lipoprotein (LDL)-cholesterol, cholesterol/HDL ratio, non-HDL cholesterol
 - o HbA_{1c}
 - o Mg
 - Mg should only be performed at Visit 1 (Screening)
 - Thyroid function tests

- Thyroid stimulating hormone (TSH) and reflex free T4
- Thyroid function tests should only be performed at Visit 1 (Screening)
- o Vitamin B12
 - Vitamin B12 should only be performed at Visit 1 (Screening)
- o Prolactin
 - Prolactin results should be blinded to the Investigator and the Sponsor after Baseline. Results will be monitored by an independent Medical Monitor from the Contract Research Organization (CRO).
- o Creatine kinase (CK)/creatine phosphokinase (CPK)
- Pregnancy test
 - A serum pregnancy test should only be performed at Visit 1 (Table 6–1) for women of childbearing potential
 - A urine pregnancy test should be performed at all designated visits after Visit 1
 (Table 6-1) for women of child-bearing potential
 - If urine cannot be obtained in women of childbearing potential, a serum pregnancy test should be done in its place
- Hematology tests
 - Complete blood count (CBC) including:
 - White blood cell (WBC) count
 - Complete differential (relative and absolute)
 - Hematocrit (Hct), hemoglobin, red blood cells (RBC), platelets
 - Reticulocyte count
- Urinalysis
 - o Blood, RBCs, WBCs, protein, glucose, ketones, specific gravity, pH
 - Reasonable efforts should be made to collect a urine sample from all subjects. When collection of a urine sample proves impractical or impossible (e.g., because the subject is incontinent or unable to cooperate), failure to collect a urine sample should be recorded in the subject's eCRF, and will not be considered a protocol deviation.

• Urine toxicology (drug) screen

O Urine toxicology (drug) screen will test for controlled substances. The following controlled substances may be tested with a urine toxicology screen according to the schedule presented in Table 6–1: amphetamine, barbiturates, benzodiazepines, cocaine, methadone, morphine/opiates, methamphetamine, marijuana (tetrahydrocannabinol [THC]), phencyclidine (PCP), ecstasy (3,4-methylenedioxymethamphetamine [MDMA]). Negative drug screens are required for study eligibility.

- A urine toxicology dipstick should be used at the Baseline and Week 3 visits. At the Baseline visit, the urine toxicology dipstick should be performed before randomization.
- Subjects who test positive and have a valid prescription for a controlled substance may be retested if they agree to abstain from the medication for the length of their participation in the study. The repeat test, and any other tests, must be negative for them to participate in the study.

Laboratory evaluations will be completed according to the schedule presented in Table 6–1 and procedures detailed in the study laboratory manual. Additional safety testing may be performed at the discretion of the Investigator or designee.

Table 6–1 Safety Laboratory Evaluations

Visit	Tests
Visit 1 (Screening)	CHEM, CBC, UA, urine toxicology screen, and serum pregnancy test
Visit 2 (Baseline)	CHEM, CBC, UA, urine toxicology screen and dipstick, urine pregnancy test, and PK blood draws
Visit 3 (Week 1)	PK blood draws
Visit 5 (Week 3)	CHEM, CBC, UA, urine toxicology dipstick, urine pregnancy test, and PK blood draws
Visit 8 (ET/EOT)	CHEM, CBC, UA, urine toxicology screen and dipstick, urine pregnancy test, and PK blood draws

Abbreviations: CBC=complete blood count; CHEM=clinical chemistry serum tests; EOT=end of treatment; ET=early termination; PK=pharmacokinetic; UA=urinalysis

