- 6. Has a positive urine drug test at Screening or Baseline or positive urine drug dipstick test result at Baseline (Day 1). For study eligibility, the urine toxicology (drug) screen (UDS) must be negative for any substance of which the subject does not have a valid prescription.
- 7. Has met DSM-5 criteria for substance use disorders within the last 6 months prior to Baseline
- 8. Has been treated once or several times for ≥2 weeks for irritability with an adequate dose of any antipsychotic treatment including off-label medication and has discontinued due to lack of efficacy as confirmed by caregiver reports and medical records when available. Discontinuation due to lack of tolerability for antipsychotic treatments of any duration is not exclusionary.
- 9. Has a current comorbid diagnosis of bipolar disorder, schizophrenia, major depressive disorder, substance use disorder, Rett syndrome, or fragile-X syndrome, as confirmed by the Mini International Neuropsychiatric Interview for Children and Adolescents (MINI-KID) at Screening. ADHD and anxiety disorders are exclusionary if they are the primary disorder, or are not stable or adequately treated.

Medical Criteria

- 10. Has any of the following:
 - a. a confirmed genetic disorder associated with ASD

> b. a cognitive and/or behavioral disturbance or profound intellectual disability (IQ≤50) documented at any time before or at Screening (measured and documented standardized, individualized, test of intelligence)

- 11. Has a history of seizures, unless seizure-free and off epileptic drugs for at least 6 months prior to Screening
- 12. Has any condition that, in the opinion of the Investigator, would interfere with the ability to comply with study instructions, or that might confound the interpretation of the study results or put the subject at undue risk
- 13. Has current evidence, or history within the previous 12 weeks prior to Screening, of a serious and/or unstable psychiatric, neurologic, cardiovascular, respiratory, gastrointestinal, renal, hepatic, hematologic, or other medical disorder, including cancer or malignancies that in the judgment of the Investigator would jeopardize the safe participation of the subject in the study
- 14. Clinically significant finding(s) on physical examination determined by the Investigator to pose a health concern to the subject while on study
- 15. Weight < 15 kg

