	RESTRICTED alprazolam lorazepam midazolam oxazepam temazepam triazolam	• Mild sedation is allowed exceptionally for ECGs and blood draws during the study (e.g., alprazolam at a pediatric-appropriate dose per age, and the lowest dose deemed necessary by the Investigator) just in cases when the subject's agitation/anxiety does not allow a safe and accurate measurement and the Investigator, with agreement from the caregiver, considers it safe and appropriate for the subject.

Final Version: 1.0 Date: 21 December 2022

Medication Class	Medicationa	Prohibition/restrictions
		 Short- or medium-acting benzodiazepine may be used for acute anxiety May not be used within 12 hours prior to an assessment visit Lorazepam, in doses according to age, may be used as a rescue medication for a maximum of 7 consecutive days. Reassessment and discussion with Medical Monitor is required if needed beyond 7 days. If lorazepam is not available, another benzodiazepine from the restricted list may be used
Beta blockers	PROHIBITED • propranolol	Prohibited at study entry and throughout the treatment period
Centrally-acting alpha-agonist hypotensive agents	PROHIBITED • clonidine	Prohibited at study entry and throughout the treatment period
Centrally-acting alpha _{2A} adrenergic receptor agonists	PROHIBITED • guanfacine	Prohibited at study entry and throughout the treatment period
Hypnotics and sleeping agents	PROHIBITEDeszopiclonezolpidemzopiclone	Prohibited at study entry and throughout the treatment period
	RESTRICTED • melatonin • ramelteon • zaleplon	May not be used within 12 hours of a cognitive assessment, and efforts should be made to limit agents to lowest dose for the shortest time needed. ○ Melatonin is allowed (≤5 mg/day) for insomnia
Non-stimulant ADHD medications	RESTRICTED • atomoxetine	Allowed if stable for at least 12 weeks prior to Screening and the dose is expected to remain the same throughout the duration of the study
Opioids	PROHIBITED • methadone	Prohibited at study entry and throughout the treatment period
Serotonin antagonists	PROHIBITED • cyproheptadine	 Prohibited throughout the treatment period Must be discontinued at least 3 weeks prior to the Baseline visit
Stimulants and wake-promoting agents	RESTRICTEDamphetamine saltsarmodafinil	Allowed if stable for at least 12 weeks prior to Screening and the dose is expected to remain the same throughout the duration of the study

Final Version: 1.0 Date: 21 December 2022

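### Section 6.4.5 bars, unless they stop treatment, children whose prescribed amphetamine product turns the drug screen positive, although Appendix A allows that drug at a stable dose and Exclusion 6 (itself ambiguous) exempts valid prescriptions

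*Protocol*

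**What the plan says.** Three parts of the protocol govern a positive drug test in a child with a prescription.

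- **Section 6.4.5, urine toxicology.** The substances that may be tested include "amphetamine, barbiturates, benzodiazepines, cocaine, methadone, morphine/opiates, methamphetamine". The rule is unqualified: "Negative drug screens are required for study eligibility". For prescription holders it adds: "Subjects who test positive and have a valid prescription for a controlled substance may be retested if they agree to abstain from the medication". Abstention is to last as long as the subject is in the study. The next condition is: "The repeat test, and any other tests, must be negative for them to participate in the study".
- **Exclusion 6 (synopsis and Section 4.2).** Sentence 1 excludes a subject who "Has a positive urine drug test at Screening or Baseline or positive urine drug dipstick test result at Baseline (Day 1"). Sentence 2 says that "the urine toxicology (drug) screen (UDS) must be negative for any substance of which the subject does not have a valid prescription". It sets no abstinence condition.
- **Appendix A, stimulants.** Amphetamine salts and lisdexamfetamine are restricted, not prohibited: "Allowed if stable for at least 12 weeks prior to Screening and the dose is expected to remain the same" for the duration of the study.

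Table 6-1 lists at Baseline "CHEM, CBC, UA, urine toxicology screen and dipstick, urine pregnancy test, and PK blood draws", so both the laboratory screen and the dipstick apply before randomisation.

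**The concern.** Eligibility rules should give one answer for each child. ADHD is an allowed comorbidity (Inclusion 10), and Appendix A plainly foresees children who stay on a stable stimulant. Yet Section 6.4.5 tells the site that such a child, if the screen is positive for amphetamine, may enter only by giving the drug up.

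A site that follows Section 6.4.5 screen-fails a child whom Appendix A admits, or offers the family abstention from a permitted medicine in order to join a trial. A site that follows Appendix A and the exception in Exclusion 6 enrols the same child. If Section 6.4.5 were later held to govern, Section 10.6 would make that enrolment a major protocol deviation and require discontinuation unless that posed an unacceptable medical risk.

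**Working it through.** The plan states no figure on this point, so the check is to apply each rule to one case: a child with ASD and stable ADHD, on prescribed amphetamine salts at an unchanged dose for at least 12 weeks before Screening, whose urine is positive for amphetamine.

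| Rule | Result |
|---|---|
| Appendix A, stimulant row | Allowed; the dose is expected to stay the same |
| Exclusion 6, sentence 2 | Screen passes; the substance is prescribed |
| Exclusion 6, sentence 1, read alone | Excluded; the Baseline dipstick is named separately |
| Section 6.4.5 | Excluded, unless the drug is stopped for the whole study and the retest is negative |

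**Appendix A against Section 6.4.5.** One expects the same dose throughout, the other no drug throughout. Both cannot be met. This is the firmest part of the conflict.

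**Exclusion 6 against Section 6.4.5.** Sentence 2 lets a prescribed positive through; Section 6.4.5 does not.

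**Inside Exclusion 6.** Sentence 2 can be read as qualifying sentence 1, since otherwise it does little. But sentence 1 covers any positive test and a positive Baseline dipstick, while sentence 2 names only the UDS. Read literally, a prescribed user could pass on the screen and fail on the dipstick.

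**Does the abstain route work?** It meets three other criteria.

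- *Exclusion 2* bars a medication change within 4 weeks (28 days) of Baseline. If the drug is stopped immediately after a positive Screening test, the standard 28-day maximum leaves 28 − 28 = 0 days' margin. The extended 35-day maximum leaves 35 − 28 = 7 days. The single rescreening in Section 4.3 can remove this timing obstacle.
- *Exclusion 9* bars ADHD that is unstable or inadequately treated. Stopping an effective stimulant risks creating that state, and rescreening does not help.
- *Inclusion 13* says investigators should not withdraw a medicine solely for enrolment unless stopping is clinically appropriate. A negative retest is not a clinical reason.

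**Which permitted drugs are caught?** Amphetamine salts are, if amphetamine is tested. Lisdexamfetamine is caught on the assumption that it gives a positive amphetamine result. Restricted benzodiazepines possibly are, because Appendix A permits some uses and the class is on the list. Methylphenidate, modafinil, armodafinil and atomoxetine are not listed.

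**Does any text rank the rules?** Section 4 defines eligibility by the listed criteria, but Section 6.4.5 states its own eligibility condition. Neither yields to the other.

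**The case against.** The best reply is that the protocol already has a way to settle such cases. Section 3.1.1 encourages the investigator and Medical Monitor to discuss eligibility so that decisions are uniform, with documented sign-off, and Section 4.8.2.1 sends medication questions to the Medical Monitor. Deciding which text applies is not a waiver. That is fair, and it may limit the problem in practice. But Section 3.1.1 also requires decisions to be consistent with the protocol, and here the protocol gives two answers.

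Other points stand in part. Section 6.4.5 says only that the listed substances may be tested, so whether amphetamine is on the panel in use depends on material not in these documents. Abstaining is voluntary, whereas Inclusion 13 restrains the investigator. These points make the consequences conditional; they do not reconcile the texts.

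A reader might infer that Exclusion 6 is clear and that only Section 6.4.5 is at fault. The documents do not support that, because sentence 1 of Exclusion 6, read alone, also bars the child. A reader might also take the SAP's stimulant-use subgroup (Section 12.5) and adverse-event summary (Section 14.1) as proof that amphetamine users were expected. They suggest that stimulant users were, but the drug class is broad and could be filled by allowed drugs that are not on the listed panel.

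**Conclusion.** The point holds as an internal inconsistency: Section 6.4.5, as written, gives the wrong result for a child whom Appendix A and sentence 2 of Exclusion 6 admit. Confidence is highest for the clash with Appendix A. The clash with Exclusion 6 depends on reading its second sentence as qualifying its first.

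The size is unknown. The documents give no rate of prescribed amphetamine use and do not show that sites would differ. The number of scheduled drug tests does not measure how many children are affected. The conclusion assumes that amphetamine is tested; amphetamine salts alone are then enough to produce the conflict.

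A reader might infer bias in the treatment comparison. None is supported: eligibility is settled before blinded assignment, and the sample size and type I error rate are untouched. What is at stake is who enters, whether a child is encouraged to stop a permitted medicine, and whether an enrolment is later classed as a major deviation. The wording should be changed.

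**What to change.** 1. In Section 6.4.5 and in sentence 1 of Exclusion 6, for both the laboratory screen and the dipstick, state: *A positive result does not exclude a subject when it is explained by a valid prescription for a medication that is not prohibited by Appendix A or B and is used within their conditions.* Referring to both appendices and to medications not prohibited, rather than to Appendix A alone, avoids narrowing the present exception more than needed.
2. Limit abstain-and-retest to prescribed controlled substances that are prohibited or are used outside those conditions, and only where stopping is clinically appropriate (Inclusion 13) and compatible with Exclusion 2.
3. Carry the wording into the synopsis and the Italian country-specific amendment. Aligning SAP Section 14.2, which repeats the abstain sentence, is optional, since it sets no eligibility rule.

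The cost is a wording amendment, submitted to IRBs/ECs and, where required, to regulators in about eight countries. It can be bundled with the next amendment and adds no visits, procedures or patients.
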